6.2. Background Characteristics

6.2.1. Participant Disposition

A disposition table will be provided with the number of study participants in:

- All-Randomized Set
- FAS
- Safety Analysis Set
- PK Analysis Set
- Immunogenicity Analysis Set

The number and percentage of study participants (based on the FAS) in each of the following disposition categories will be summarized by VIR-3434 treatment cohort, placebo, and overall, for each of Part A, B, C, and D.

- Completed Follow-up (24 weeks or 8 weeks for Part A or Part B, C, and D respectively)
- Completed Study
- Prematurely discontinued study and the primary reason for discontinuation
- Entered extended follow-up (if applicable)

A listing will be provided for subjects who discontinued follow-up or who discontinued study with reason for discontinuation.

6.2.2. Demographics and Baseline Characteristics

Demographic and baseline characteristics will be summarized based on the FAS by VIR-3434 dosing cohort, placebo, and overall, for each of Part A, B, C, and D.

Demographic data will include the following:

- Age at baseline (in years)
- Age group (< 30, ≥ 30 and < 40, ≥ 40 and < 50, ≥ 50)
- Sex (female and male)
- Ethnicity (Hispanic or Latino, not Hispanic or Latino, Not Reported, Unknown)
- Race (White, Black or African American, Asian, American Indian or Alaska Native, Native Hawaiian or Other Pacific Islander, Other, Not Reported)
- Country

Baseline characteristics will include the following:

For Part A and Part B, C, and D

- Weight (kg)
- Height (cm)
- BMI (kg/m²) and BMI categories (≤ 18.5, >18.5 to ≤ 25, > 25 to ≤ 30, and > 30)
- Creatinine Clearance (mL/min)

For Part B, C, and D only

- HBsAg as a continuous variable (log₁₀ IU/mL) and categories (< 1000 IU/mL, 1000 IU/mL – < 3000 IU/mL, 3000 IU/mL – < 10000 IU/mL, and ≥ 10000 IU/mL)
- HBeAg as categories (HBeAg+ and HBeAg-)
- HBV DNA (part D only)
- HBcrAg
- HBV RNA
- ALT (U/L) as a continuous variable and as categories (≤ ULN, >ULN – 2×ULN, and > 2×ULN)
- Liver stiffness (kPa)
- HBV genotype

In addition, data listings will be provided for:

- Informed consent
- Inclusion/Exclusion criterion for subject with any such violations

6.2.3. Medical History

Medical history will be provided in an individual participant listing.

6.2.4. Prior and Concomitant Medications

Medications will be coded using the World Health Organization Drug Dictionary (WHODD, March 2022) and are categorized as follows:

Prior medication: any medication that was administered prior to the first dose of study intervention, regardless of when it ended

Concomitant medication: medication continued or newly received during the TE period

Post-treatment medication: medication continued or newly received after the TE period

A given medication may be classified as follows: prior, concomitant, post-treatment, both prior and concomitant, both concomitant and post-treatment, or prior, concomitant, and post-treatment.

If a medication start date is at or after the dosing date of study intervention, then the medication will be summarized as concomitant medication regardless of whether the medication end date is missing or not. If a medication end date is before the dosing date of study intervention, then the medication will be summarized as prior medication regardless of whether the medication start date is missing or not. A medication that started prior to dosing of study intervention and continued after dosing of study intervention will be summarized as prior medication and separately as concomitant medication.

Both prior and concomitant medications will be summarized descriptively by VIR-3434 treatment cohort, placebo, and overall, with preferred name (PN) based on the FAS, for each of Part A, B, C, and D.

If a medication has a completely missing or partially missing start/stop date and it cannot be determined whether it was taken before the dosing date of study intervention, concomitantly during the TE period, or after the TE period, it will be classified as prior, concomitant, and post-treatment. Details for imputing missing or partial start and/or stop dates of medication are described in Appendix 3.

6.2.5. Important Protocol Deviations

An important protocol deviation (IPD) is a deviation that may significantly affect the completeness, accuracy, or reliability of the study data or that may significantly affect a participant's rights, safety, or well-being. IPD rules will be developed and finalized prior to database lock and will be used to categorize any of protocol deviation events to be IPDs or not by a sponsor-blinded team.

IPDs (from the deviation log produced by the sponsor or designee) will be summarized descriptively based on the FAS and presented by VIR-3434 treatment cohort, placebo, and overall, for each of Part A, B, C, and D. Additionally, IPDs will be provided in an individual subject data listing.

6.3. Efficacy Analysis

No efficacy analysis will be conducted in this study.

6.4. Safety Analyses

Safety analyses will be based on data from the TE Period for all participants in the Safety Analysis Set, unless otherwise specified. All safety data will be included in the individual participant listings. Participants will be analyzed according to the treatment dose level they received.

The overall safety profile of the study intervention will be assessed in terms of the following safety and tolerability assessments:

- TEAEs
- Clinical laboratory
- ECG
- Vital signs
- Physical examination

Only descriptive analysis of safety will be performed, and no statistical testing will be performed.

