8.12. Local Tolerability

For all study parts, a local tolerability assessment will be performed per the Schedule of Assessments for subjects receiving study drug by SC injection. Injection site(s) will be marked and mapped for later observation and should be documented. Injection site(s) should be monitored for pain/tenderness, swelling, redness, bruising, and pruritus.

The timing of local tolerability assessments for Part A can be found in [Appendix 2](#). The timing of the local tolerability assessments for Parts B, C, and D can be found in [Appendix 3](#).

At the discretion of the investigator, unscheduled visits are permitted as needed for follow up of any unresolved local tolerability symptoms.

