- ^o Includes samples for ADA and neutralizing antibodies (NAb), as applicable. Additional unscheduled samples for immunogenicity analysis may be collected if an immunologic related event is suspected. Immunogenicity sampling beyond the planned follow-up period may occur based on emerging results. Further details can be found in Section 8.16 .
- ^p Local tolerability only needs to be assessed for subjects who are administered study drug by SC injection. On Day 1, local tolerability should be assessed at approximately 1 hour post-dose. At the discretion of the investigator, unscheduled visits are permitted as needed for follow up of any unresolved local tolerability symptoms.
- ^q All AEs related to screening activities must be collected starting at the time of consent; any other events occurring during the screening period should be reported as medical history. All SAEs must be collected from the time of consent onwards. Further details can be found in Section 9.3.

APPENDIX 3. PART B, C, AND D SCHEDULE OF ASSESSMENTS FOR SAD COHORTS IN SUBJECTS WITH CHRONIC HBV INFECTION WITHOUT CIRRHOSIS

Part B, C, and D														
Study Stage	Screening	Dosing Day ^a	Post-dose Follow-up Period							Extended Follow-up Period ^b				
Study Visit Week					W1		W2	W4	W8/ET ^c	W12	W16	W24	W32	W40 / EF ^d
Study Visit Day±Visit Window	D -42 to -1	D1 ^e	D2	D4+1	D8±1	D11±1	D15±2	D29±2	D57±7	D85 ±7	D113 ±7	D169 ±7	D225 ±7	D281 ±7
Informed consent	X													
Demography	X													
Medical history including HBV genotype ^f	X													
Inclusion/exclusion criteria	X	X ^g												
Full physical examination ^h	X			X					X					
Symptom-directed physical examination		X	X		X		X	X						
Body weight	X													
Height	X													
Vital signs ⁱ	X	X	X	X	X		X	X	X					
Safety ECGs ^j	X													
Pregnancy test ^k	X	X						X	X	X	X	X	X	X
FibroScan ^l	X													
Screening viral serology ^m	X													
Liver Function Tests ⁿ	X	X	X	X	X		X	X	X	X	X	X	X	X
Serum Chemistry ⁿ	X	X	X	X	X		X	X	X	X	X	X	X	X

Part B, C, and D														
Study Stage	Screening	Dosing Day ^a	Post-dose Follow-up Period							Extended Follow-up Period ^b				
Study Visit Week					W1		W2	W4	W8/ET ^c	W12	W16	W24	W32	W40 / EF ^d
Study Visit Day±Visit Window	D -42 to -1	D1 ^e	D2	D4+1	D8±1	D11±1	D15±2	D29±2	D57±7	D85 ±7	D113 ±7	D169 ±7	D225 ±7	D281 ±7
Hematology ⁿ	X	X	X	X	X		X	X	X					
Coagulation Parameters ⁿ	X	X	X	X	X		X	X	X					
Complement testing ^{n,o}		X			X		X							

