Part B, C, and D: • Urinalysis	Day 1 (Baseline) Week 1 Week 2	1 8 15	≤1 Pre-dose [1, 11] (11, min(≥64, Ext FU Day 1)]
Part B, C, and D: • Local tolerability	Day 1 (Baseline) Day 2 Day 4 Week 1	1 2 4 8	≤1 Pre-dose [1, 3] (3, 6] (6, min(≥64, Ext FU Day 1)]
Part B, C, and D: • Physical examination	Screening (Baseline) Day 4 Week 8	<1 4 57	<1 Pre-dose [1, 30] (30, min(≥64, Ext FU Day 1)]
CCI			
Extended Follow-Up Period (Part B, C, and D)			
• Pregnancy test • Liver function test • Serum chemistry • Immunogenicity • HBsAg and Anti-HBS • HBV DNA (Part D)	Ext Week 12 Ext Week 16 Ext Week 24 Ext Week 32 Ext Week 40	85 113 169 225 281	(Ext FU Day 1, 99] (99, 141] (141, 197] (197, 253] (253, ≥288]

Table 7-1 Analysis Visit Windows for Safety and Antiviral Assessments			
Assessment	Analysis Visit¹	Target Study Day	Analysis Visit Window (in study days)^{2, 3, 4, 5}
Part B, C, and D: 
 • HBV RNA • HBcrAg 	Ext Week 12 Ext Week 24 Ext Week 32 Ext Week 40	85 169 225 281	(Ext FU Day 1, 113] (113, 197] (197, 253] (253, ≥288]
CCI			
Part B, C, and D: 
 • HBeAg and Anti-HBe 	Ext Week 40	281	(Ext FU Day 1, ≥288]

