Notes: 
¹ Visit name for analysis purpose is used to report data in tables and figures.
 
² The analysis visit windows will be applied using the following rules for both scheduled and unscheduled visits:
 
 a. If no numerical measurement is available within a visit window, the measurement will be considered missing for the visit. b. If there is more than 1 numerical measurement available within a visit window, use the following rules: 
 i. If the scheduled visit measurement will be used if it is available ii. If not, the unscheduled visit measurement closest to the target day will be used; or iii. If there are multiple unscheduled visit measurements with the same distance from the target day, the latest measurement will be used. 
³ For an assessment, e.g., laboratory, ECG and vital sign measurement collected on the date of first dose of study drug, if it cannot be determined whether the measurement is before or after the first dose:
 
 a. Scheduled measurement will be treated as pre-dose observation. b. Unscheduled measurement will be treated as post-dose observation. 
⁴ For vital signs, Day 1 will be included in the Day 1 visit window to account for the post-dose assessments on Day 1, .
 
⁵ PK analysis window will follow the protocol-defined assessment visit window.
			

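### The scheduled injection-site tolerability check has SAP visit windows but no planned summary, so local tolerability is tabulated by dose and against placebo only as far as findings are reported as TEAEs

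*SAP*

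**What the plan says.** **Collection.** Protocol 8.12 says that in all study parts "a local tolerability assessment will be performed per the Schedule of Assessments for subjects receiving study drug by SC injection", and that "Injection site(s) should be monitored for pain/tenderness, swelling, redness, bruising, and pruritus". The schedules in Protocol Appendices 2 and 3 place the check at Day 1, Day 2, Day 4 and Week 1. For Part A, a footnote to Appendix 2 adds: "Local tolerability only needs to be assessed for subjects who are administered study drug by SC injection". The same footnote gives the Day 1 timing: "On Day 1, local tolerability should be assessed at approximately 1 hour post-dose".

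**Analysis windows.** SAP Appendix 2, Table 7-1, has a "Local tolerability" entry for Part A and another for Parts B, C and D, each with Day 1 (Baseline), Day 2, Day 4 and Week 1. Note 1 to that table reads: "Visit name for analysis purpose is used to report data in tables and figures".

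**Planned analysis.** SAP 6.4 introduces its list with "The overall safety profile of the study intervention will be assessed in terms of the following safety and tolerability assessments". The list has five items: TEAEs, clinical laboratory, ECG, vital signs and physical examination. Sections 6.4.1 to 6.4.5 cover those five and nothing else. A general sentence in 6.4 sends all safety data to participant listings.

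**Protocol commitment.** Protocol 10.4 says that safety data collected from dosing to the last scheduled visit will be summarised by cohort for each dose and placebo, unless specified otherwise. SAP 6.8.1, which records departures from the protocol, does not mention local tolerability.

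**The concern.** The primary objective in every Part is safety and tolerability, and the drug is given SC in all but two enrolled cohorts. The scheduled check is the only measurement aimed directly at the injection site, made at set times in active and placebo subjects alike. As the SAP stands, these data reach a listing and no table.

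What would be tabulated instead is the set of injection-site events entered as adverse events. Neither document states that a positive finding at a scheduled check must be entered as one. TEAE tables by system organ class and preferred term also give no by-visit picture of onset and resolution. With six active subjects planned per cohort, a few findings recorded in the check but not as adverse events could change how a dose level looks.

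**Working it through.** The plan states no figure on this point, so the check consists of tracing the data from collection to output and counting who is affected.

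**1. From collection to output**

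| Step | Place | Local tolerability included? |
|---|---|---|
| Collection | Protocol 8.12; Appendices 2 and 3 | Yes, all SC subjects, four checks |
| Analysis windows | SAP Appendix 2, Table 7-1 | Yes, Part A and Parts B–D |
| Named safety and tolerability assessments | SAP 6.4 | No |
| Tables and figures | SAP 6.4.1–6.4.5 | No |
| Listing | SAP 6.4, general sentence | Yes, by implication |
| Recorded departure from protocol | SAP 6.8.1 | No |

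Where the SAP intends a listing alone, it generally says so: positive pregnancy tests (6.4.2) and physical examination (6.4.5) are expressly listing only, and 6.4.3 provides only a listing for ECGs. It makes no such statement for local tolerability.

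**2. Subjects affected** (SAP Tables 1 and 2 for enrolled cohorts; Protocol Tables 3 to 6 for the 6:2 allocation)

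- Enrolled SC cohorts: A 3 (1a–3a) + B 4 (1b–4b) + C 3 (1c–3c) + D 2 (1d–2d) = 12. With the two IV cohorts 4a and 5a, 14 cohorts are enrolled.
- Active: 12 × 6 = 72. Placebo: 12 × 2 = 24. Total: 72 + 24 = 96 planned.
- Scheduled checks at full attendance: 96 × 4 = 384.

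**3. Injected volume within each Part.** The reconstituted concentration is 150 mg/mL (Protocol 7.3.1). Assuming no further dilution, volume = dose / 150.

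| Part | Lowest enrolled SC dose | Highest enrolled SC dose | Ratio |
|---|---|---|---|
| A | 90/150 = 0.6 mL | 900/150 = 6 mL | 10 |
| B | 6/150 = 0.04 mL | 300/150 = 2 mL | 50 |
| C | 18/150 = 0.12 mL | 300/150 = 2 mL | about 17 |
| D | 75/150 = 0.5 mL | 300/150 = 2 mL | 4 |

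**4. Whether the windows would support a table.** In Part A, Table 7-1 labels Day 1 as pre-dose, and the Day 2 window is [1, 2]. The only Day 1 check is about 1 hour post-dose.

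- If its time is known, it falls in the Day 2 window with the true Day 2 check. Note 2 has no rule for choosing between two scheduled values in one window.
- If its timing relative to dosing cannot be determined, note 3 treats a scheduled Day 1 measurement as pre-dose, and a post-dose finding becomes a baseline value.
- Note 4 makes a Day 1 post-dose allowance for vital signs only.

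For Parts B–D the Day 2 window is [1, 3]. The Protocol Appendix 3 footnote on Day 1 timing cannot be read in the public copy, so the same conflict is not asserted there.

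**5. Placebo comparator in Part A.** The protocol synopsis pools placebo by route within each Part. The SAP safety sections say only placebo. SC placebo is 3 × 2 = 6 planned subjects; adding IV placebo (2 × 2 = 4) would give 10, of whom 4 had no SC injection and need no local tolerability check.

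**The case against.** Five points can be made on the other side.

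- **The TEAE tables already cover it.** The adverse event definition in Protocol 9.1.1 is broad enough to include a new injection-site sign. Protocol 9.3 collects all adverse events after dosing through Week 24 (Part A) or Week 8 (Parts B–D). SAP 6.4.1 tabulates TEAEs by cohort and placebo, with further tables by maximum severity and for related events. This stands. A reader might infer that injection-site tolerability is never compared by dose or with placebo; the documents do not support that, because events entered as TEAEs are compared. Nor do they show that entry varies between sites: the case report form and its completion guidelines may settle it, and they are not available here.
- **A window does not promise a table.** This also stands. Physical examination and pregnancy tests have windows but are listing only, and urinalysis has windows in Parts B–D but is only listed. The windows alone would not make the case.
- **No endpoint is left unanalysed.** True: local tolerability is not a named endpoint in Protocol 4 or SAP 2.2, and the items named in Protocol 10.4 do not include it. It does not follow that no commitment is affected, because the general sentence in Protocol 10.4 covers all post-dose safety data.
- **The SAP may be the place where it is otherwise specified.** This is possible, but the SAP would then need to say so, and 6.8.1 is silent.
- **The form of the data is assumed.** Protocol 8.12 names five signs but gives no grading scale and does not show that each is a separate data field. This stands as an assumption behind the proposed table.

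**Conclusion.** The point holds as a gap in reporting. A scheduled assessment that bears directly on the primary tolerability objective is collected in 12 SC cohorts, about 96 planned subjects, and has no specified summary by visit, dose or placebo. Tabulation rests wholly on findings being reported as TEAEs, Protocol 10.4 points the other way, and no change is recorded.

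It is a cheap improvement to a descriptive plan. It does not put a named endpoint at risk.

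The counts assume the planned 6:2 allocation; SAP 3.1 says approximately 8 per cohort, and 384 checks further assumes full attendance. The volume ratios assume undiluted drug. Doses may be split over more than one syringe (Protocol 7.3.5), so volume per site is unknown. A reader might set 6 mg against 900 mg and infer a 150-fold volume range, but that joins Part B patients to Part A healthy subjects, while the SAP reports by Part. The supportable within-Part ranges are about 10-fold (A), 50-fold (B), 17-fold (C) and 4-fold (D).

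**What to change.** 1. Add a local tolerability subsection to SAP 6.4 and add the item to the list there. For each Part, give n (%) with each of the five signs and with any sign, at each post-dose check and at any time through Week 1, by SC cohort and SC placebo. In Part A, exclude IV placebo.
2. Correct Table 7-1 for Part A so that the check at about 1 hour post-dose is kept as a Day 1 post-dose value and falls neither in the Day 2 window nor at baseline. Check the same point for Parts B–D against the unredacted schedule.
3. State an explicit last day for the any-time row, because the Week 1 windows run on to the end of follow-up or the start of extended follow-up.
4. State whether positive findings are also entered as adverse events, so that the new table and the TEAE tables can be read together.
5. If a listing alone is intended, say so and record it in SAP 6.8.1.

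The cost is one descriptive table per Part and a small edit to the windows, before database lock. It needs no new data, provided the five signs are captured as separate fields.

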6.4.1. Adverse Events

For analysis purposes, AEs will be classified as TEAEs or post-treatment AEs, defined as follows:

Pre-treatment AE: any AE that occurred before the administration of study intervention (which is collected and will be summarized in medical history).

TEAE: any AE that worsened (either in severity or seriousness) or that was newly developed at or after the administration of study intervention through the end of the TE period.

Post-treatment AE: any AE that worsened (either in severity or seriousness) or that was newly developed after the TE period.

For AEs with completely missing or partially missing start dates, if there is no clear evidence that the AEs are pre-treatment or post-treatment, the AEs will be classified as TEAEs. Details for imputing missing or partial start dates of adverse events are described in Appendix 4.

An overview of all TEAEs by VIR-3434 treatment cohort, placebo, and overall, for each of Part A, B, C, and D, will be summarized in the following categories:

- Number of TEAEs
- Participants with any TEAEs
- Participants with TEAEs by maximum severity (toxicity grade)
- Participants with TEAEs leading to study discontinuation
- Participants with Grade 3/4/5 TEAEs

- Participants with (study intervention) related TEAEs
- Participants with serious TEAEs
- Participants with (study intervention) related serious TEAEs
- Participants with TEAE leading to death

The following summary tables of TEAEs will be presented by MedDRA System Organ Class (SOC) and Preferred Term (PT) using frequency counts and percentages (i.e., number and percentage of participants with an event), and by VIR-3434 treatment cohort and placebo, for each of Part A, B, C, and D:

- All TEAEs
- Grade 3/4/5 TEAEs
- TEAEs by maximum severity (toxicity grade)
- TEAEs leading to study discontinuation
- Related TEAEs
- Serious TEAEs
- Related serious TEAEs
- TEAEs leading to death

In addition, the following TEAEs tables will be also summarized by MedDRA PT only in order of descending incidence by VIR-3434 treatment cohort and placebo:

- All TEAEs
- TEAEs that occurred $\geq 5\%$
- Grade 3/4/5 TEAEs

When summarizing the number and percentages of participants, participants with multiple occurrences of the same adverse event or a continuing adverse event will be counted once, and only the maximum severity (highest grade) level will be presented in the severity summaries, and the study intervention related relationship in the relationship summaries.

All AEs, including TEAEs and post-treatment AEs, will be presented in an individual participant data listing based on the Safety Analysis Set. In addition, a listing containing individual participant adverse event data for TEAEs leading to study discontinuation, Grade 3/4/5 TEAEs, SAEs and all deaths will be provided separately, with a flag indicating the TEAE status for SAEs and deaths.

6.4.2. Clinical Laboratory

Clinical laboratory data collected (through central laboratories only, unless otherwise specified) will be analyzed using both quantitative and qualitative methods and presented by VIR-3434 treatment cohort and placebo, for each of Part A, B, C, and D. The analysis will be based on values reported in conventional units.

For the treatment-emergent laboratory measurements, the observed values and change from baseline values of the continuous hematology, serum chemistry, and coagulation results will be summarized descriptively (n, mean, SD, median, min, max) at each visit.

For ALT, AST, total bilirubin, lymphocytes, neutrophils, platelets, and INR, mean (\pm SD) of the observed values will be plotted by visit and by each VIR-3434 treatment cohort and placebo for each of Part A, B, C, and D.

The Common Terminology Criteria for Adverse Events (CTCAE, v5.0) will be used as the reference on grading scale to assign severity (toxicity) grades (1 to 4) to abnormal results for the laboratory of interest as shown in Appendix 5. Grade 0 refers to the normal values that do not meet the criteria of laboratory abnormalities.

For treatment-emergent laboratory abnormalities, the number and percentage of participants who met at least 1 threshold criterion of severity grade will be summarized by VIR-3434 treatment cohort and placebo for each of Part A, B, C, and D, based on the most severe postdose abnormality grade during TE period for a given laboratory test. The threshold of severity grade shifted from baseline will also be summarized for selected laboratory tests.

In addition, a separate listing containing individual participants with hematology, chemistry, coagulation, and urinalysis values will be provided based on the Safety Analysis Set by subject ID and visit in chronological order including data collected from both scheduled and unscheduled visits. Values falling out of the relevant normal range (between the value of LLN and ULN) or having the severity grade of 1 or higher on laboratory abnormalities will be flagged as appropriate.

Results of positive urine/serum pregnancy test will be listed in an individual participant data listing only.

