Results from a non-GLP PK study in cynomolgus monkeys (PK-3434-0109) was used to develop a linear two-compartment PK model which was further scaled to human using allometry. Human VIR-3434 serum clearance and volume of distribution were predicted to be approximately 65.7 mL/day and 2.43 L, respectively, in the central compartment and 612.7 mL/day and 2.85 L, respectively, in the peripheral compartment. Based on these estimations, terminal elimination half-life of VIR-3434 in humans was predicted to be approximately 58 days. These parameters were used to simulate human PK profiles over the proposed Part A dose range of 90 to 900 mg administered by SC injection and 900 mg and 3,000 mg administered by IV infusion. Additional information is provided in the Investigator’s Brochure.

Table 1: Part A Dose Escalation Plan

Study Part	Cohort	Active:Placebo	Dose (Route)	Frequency of Administration
A	1a	6:2	90 mg (SC)	Once
	2a	6:2	Up to 300 mg (SC)	Once
	3a	6:2	Up to 900 mg (SC)	Once
	4a (Optional)	6:2	Up to 900 mg (IV)	Once
	5a (Optional)	6:2	Up to 3,000 mg (IV)	Once

IV = intravenous; SC = subcutaneous.

Part B: Single Ascending Dose Study in Subjects with Chronic HBV Infection

In Part B, subjects with chronic HBV infection will receive a single dose of study drug. The presence of the therapeutic target of VIR-3434, HBsAg, in subjects with chronic HBV infection alters the potential risks of VIR-3434 administration. Potential risks include immune complex disease due to the formation of antigen-antibody complexes and hepatotoxicity due to elimination of infected hepatocytes via ADCC/ADCP and/or a “vaccinal effect”. To minimize risks to subjects, Part B will be conducted in subjects who are on NRTIs and have HBV DNA < 100 IU/mL at screening, and who have good hepatic reserve and low levels of hepatic inflammation, as determined by lack of significant fibrosis/cirrhosis and ALT $\leq 2 \times$ ULN.

Available non-clinical toxicology and PK/PD data, as well as experience with molecules having similar characteristics, were taken into account when selecting the starting dose and dose escalation scheme for VIR-3434 in subjects with chronic HBV infection. The proposed starting dose of 6 mg (approximately 0.1 mg/kg) is supported by the following rationale:

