- Parts B and C will enroll subjects who are on NRTIs and have HBV DNA < 100 IU/mL at screening and have good hepatic reserve and a low level of hepatic inflammation at baseline as determined by the following attributes: ALT or AST $\leq 2 \times$ ULN, no history of hepatic decompensation, and lack of significant fibrosis and cirrhosis.
- Part D, which will enroll subjects who are not on NRTIs and have HBV DNA $\geq 1,000$ IU/mL and any HBsAg level, will be initiated only following SRC review of available safety data through the Week 4 visit for the cohort of subjects in Part B who are receiving a matching or higher dose.
- Two sentinel subjects will be randomized 1:1 to VIR-3434 or placebo and dosed. These sentinel subjects will be monitored through at least 72 hours post-dose and if the

investigator(s) have no safety concerns, the remaining 6 subjects in the same cohort will be dosed 5:1 (5 active and 1 placebo).

- Dose escalation will occur after SRC review of available safety data up to 4 weeks after dose administration to account for the anticipated timing of potential immune complex disease and hepatotoxicity due to the elimination of infected hepatocytes via ADCC/ADCP and/or cytotoxic T-cells induced via a vaccinal effect.
- Safety monitoring, including liver function tests, urinalysis, renal function, vital signs, and physical examination findings, is designed to detect evidence of VIR-3434-associated immune adverse events.

The risk/benefit assessment for subjects with chronic HBV is based on the balance between potential safety issues associated with the presence of antigen (HBsAg) and the anticipated benefits of a treatment modality designed to effectively reduce HBsAg, an immune tolerogen, and lead to clearance of infected hepatocytes. There is no approved therapy that reduces serum HBsAg in a substantial proportion of patients. If serum HBsAg can be effectively reduced in combination with clearance of infected hepatocytes, the anticipated safety profile of VIR-3434 would offer a favorable risk-benefit profile in patients with chronic HBV infection enrolled in Parts B, C, and D of the study.

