APPENDIX 9. CLINICAL LABORATORY ASSESSMENTS

Hematology	
Complete blood count with differential	
Chemistry	
Albumin	Creatinine clearance
Blood urea nitrogen (BUN)	Gamma glutamyl transferase (GGT)
Calcium	Glucose
Carbon dioxide/bicarbonate	Lactate dehydrogenase (LDH)
Chloride	Potassium
Creatine kinase ^a	Sodium
Creatinine	
Liver Function Tests	
Alkaline phosphatase (ALP)	Aspartate aminotransferase (AST)
Alanine aminotransferase (ALT)	Bilirubin (total and direct)
Coagulation Parameters	
International normalized ratio (INR) time	Prothrombin
Urinalysis	
Bilirubin	Proteins
Glucose	Red blood cells (RBCs)
Ketones	Screen for drugs of abuse
Leukocytes	Specific gravity
Microscopy (if clinically indicated)	Urobilinogen
Nitrite	Visual inspection for appearance and color
pH	
Pregnancy Testing (WOCBP only)	
Beta-human chorionic gonadotropin	Urine pregnancy test
Screening Viral Serology	
Hepatitis B, C ^b , and Delta	Human immunodeficiency virus I and II

^aOnly required if ALT and/or AST is elevated >2x the predose Day 1 baseline value

^bSubjects in Parts B, C, and D with positive HCV screening serology may have HCV RT-PCR performed to determine eligibility

Signature Page for VV-CLIN-000053 v7.0

Approval Task	PPD
---------------	-----

Signature Page for VV-CLIN-000053 v7.0

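### Parts B–D: complement has no planned summary, urinalysis is only listed, and neither is graded, so the laboratory markers tied to immune complex disease cannot reach the by-arm laboratory-abnormality table

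*SAP*

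**What the plan says.** Protocol section 2.3.2, on Part B: "Potential risks include immune complex disease due to the formation of antigen-antibody complexes". Section 2.4 describes the monitoring meant to address such risks; besides liver tests it names "urinalysis, renal function, vital signs, and physical examination findings, is designed to detect evidence of VIR-3434-associated immune adverse events".

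The Parts B–D schedule (protocol Appendix 3) has a row for "Complement testing" at Day 1, Week 1 and Week 2, and a urinalysis row at screening and the same three visits. Footnote o, attached to both rows, allows extra samples after dosing when immune complex disease is suspected. Protocol Appendix 8 includes both tests in the possible work-up of a suspected case.

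The number of subjects with clinical laboratory abnormalities is a primary endpoint (protocol section 4.2). SAP section 6.4.2 serves it in three ways:

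- By-visit descriptive summaries: "change from baseline values of the continuous hematology, serum chemistry, and coagulation results will be summarized descriptively".
- A count, by VIR-3434 cohort and placebo, of subjects reaching a severity grade, with the grades set out in SAP Appendix 5.
- A listing: "individual participants with hematology, chemistry, coagulation, and urinalysis values will be provided". Out-of-range values are flagged.

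SAP section 6.1 adds a general rule that all individual data of randomized participants are listed.

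**The concern.** Immune complex disease is one of the two risks that the protocol attributes to the presence of HBsAg; the other is hepatotoxicity. The two are handled unevenly. Liver tests are graded and counted by arm, and ALT, AST and total bilirubin are also plotted by arm. Complement and urinalysis, the tests that footnote o links to immune complex disease, get no summary and no grade.

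The adverse event tables do not fill this gap for silent changes. Under protocol section 9.1.1, laboratory abnormalities without signs or symptoms are not recorded as adverse events, because they are expected to be captured as laboratory abnormalities. Section 9.1.3 adds those that need intervention, but nothing milder. The SAP's laboratory tables then do not capture them either. Followed exactly, the plan yields a primary laboratory endpoint that leaves out the markers for a named risk.

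**Working it through.** The SAP gives no figure to reproduce. The check is which output each test can reach in Parts B–D.

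| SAP output | Creatinine, creatinine clearance | Urinalysis | Complement |
|---|---|---|---|
| By-visit summary (6.4.2) | Yes, as serum chemistry | No | No |
| Grade (Appendix 5) | Yes | No row for urine protein or urine red cells | No row |
| Graded-abnormality count by arm (6.4.2) | Yes | Not possible without a grade | Not possible without a grade |
| Visit window (Appendix 2, Table 7-1) | Yes | Yes: Day 1, Week 1, Week 2 | None visible; some rows are redacted |
| Listing | Named in 6.4.2 | Named in 6.4.2, flagged | Only through the general rule in 6.1 |

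Note 1 to Table 7-1 says that analysis visit names serve tables and figures. Urinalysis has such visits, yet no urinalysis table is specified, which suggests an oversight.

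**Size.** Inputs:

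- Enrolled HBV cohorts (SAP Table 2): 4 in Part B, 3 in Part C, 2 in Part D; 4 + 3 + 2 = 9.
- Subjects per cohort: about 8 (SAP section 3.1), planned as 6 active and 2 placebo (protocol Tables 4 to 6).
- Scheduled post-dose draws: 2 (Week 1 and Week 2). Day 1 is predose, by footnote e of protocol Appendix 3, so it is baseline.

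Results:

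- Subjects: 9 × 8 = 72, of whom 9 × 6 = 54 active and 9 × 2 = 18 placebo.
- Post-dose complement results: 72 × 2 = 144.
- From VIR-3434 subjects: 54 × 2 = 108. From placebo: 18 × 2 = 36.
- Urinalysis follows the same post-dose schedule, so another 144 scheduled urinalysis samples are listed but not tabulated.

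Counting the Day 1 draw as well gives 72 × 3 = 216 complement results, but the 72 baseline values cannot themselves show a treatment effect.

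**What a table adds.** The protocol synopsis combines placebo subjects across cohorts by route within each Part. On full cohorts the comparators are 4 × 2 = 8 placebo subjects in Part B, 3 × 2 = 6 in Part C and 2 × 2 = 4 in Part D, each set beside cohorts of 6 active subjects. A modest shift could be seen in that comparison; a reader of subject-by-subject listings would have to assemble it by hand.

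**The case against.** Several stronger readings are tempting, and the documents do not support them.

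- *No table shows immune complex disease by arm.* This is too broad. SAP section 6.4.1 tabulates all, related, serious and Grade 3 to 5 treatment-emergent events by system organ class and preferred term, by cohort and placebo. Serum sickness or glomerulonephritis reported up to Week 8 would appear there.
- *A finding of no signal would rest on clinical events alone.* Creatinine and creatinine clearance are graded and counted by arm, and vital signs are summarised by visit.
- *The samples go unused.* Urinalysis is listed with flags, and complement falls under the general listing rule. The Safety Review Committee reviews available laboratory safety data through 4 weeks before each Part B escalation, which covers the Week 1 and Week 2 draws. Both tests may also inform individual work-ups.
- *The SAP contradicts the protocol.* Protocol section 10.4.2 promises summaries of selected laboratory data only and defines abnormalities by CTCAE grade. This is an omission. Whether CTCAE grades these tests cannot be settled from the documents.

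The case for leaving the plan alone has some weight. The study is descriptive, cohorts are very small, and flagged urinalysis listings may be adequate for a careful reader. The link between complement and immune complex disease also has to be drawn from footnote o and Appendix 8, because section 2.4 names urinalysis but not complement. Redactions in Table 7-1 mean that a complement window may exist.

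None of this supplies a by-arm summary. SAP section 6.4.2 and Appendix 5 show no visible redaction, and creatinine does not stand in for complement, urine protein or urine red cells. The point is strongest for complement, which lacks even a named listing.

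**Conclusion.** The point holds in this limited form: no planned table shows complement or urinalysis by arm, and neither can contribute to the graded laboratory-abnormality count. Clinically reported events up to Week 8 and renal chemistry are covered.

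About 144 post-dose complement results, about 108 of them from VIR-3434 subjects, are affected. These figures assume full cohorts of 8 split 6 to 2 and no missed visits, and they exclude unscheduled samples. They count results without a table; they do not estimate how often a silent abnormality would occur, which the documents do not allow.

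This should be changed because the samples are already scheduled and the outputs are simple. It does not undermine the other safety tables.

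**What to change.** In SAP section 6.4.2 add, for Parts B, C and D, by VIR-3434 cohort and pooled placebo within each Part:

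1. Complement: observed value and change from Day 1 at Week 1 and Week 2, with the number of subjects newly below the laboratory's lower limit of normal at any post-dose sample, unscheduled ones included.
2. Urinalysis: the number of subjects with new or worsened urine protein or urine red cells compared with Day 1.

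State the abnormality criteria in advance, since Appendix 5 supplies none for these tests. Add a complement window to Table 7-1 if the redacted rows do not already hold one; the urinalysis window exists.

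The cost is SAP wording and two small descriptive tables, with no new samples or visits. With about 6 active and 2 placebo subjects per cohort, the tables must be read cautiously: one subject is a large percentage, and an absence of findings would not exclude a modest effect.
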